Patients with metastatic urothelial cancer will receive Atezolizumab intravenously at 1200mg every three weeks or Pembrolizumab at a flat dose of 200mg every three weeks (Physician's discretion). Patients will continue to receive infusions every two or three weeks for up to three years or until disease progression or until a dose limiting toxicity is reached.

Patients randomized to the radiotherapy arm will receive radiation every other day. A dose of 10 Gy x3 days will be administered.

Primary Objectives: The primary aim is to estimate the difference in best overall response (BOR; time frame: 96 weeks) rates using RECIST version 1.1, in patients with metastatic renal cell/urothelial carcinoma when treated with immunotherapy alone and immunotherapy plus radiotherapy (to a single metastatic site).

[figure not shown]
Secondary Objectives: The secondary aims are: 1) to estimate the median progression free survival and the median overall survival for patients treated with immunotherapy and immunotherapy plus radiotherapy, and 2) to assess the toxicity (per CTCAE version 4.0) of patients treated with immunotherapy and immunotherapy plus radiotherapy.

**Exploratory
(Correlatives)
Objectives:**

Exploratory analyses will include: 1) examination of an association between clinical responses and anti-tumor immune responses (cellular and humoral responses) and 2) comparison of T cell subsets within tumors and in the peripheral blood at baseline versus at the time of response evaluation.

Endpoints: The primary endpoint will be BOR (time frame: 96 weeks) rates as evaluated using RECIST version 1.1. Other end points include progression free-survival and overall survival.

SCHEMA
Please see study calendar (section 14.0) for additional screening procedures and treatment windows

- *Renal cell cancer patients – Nivolumab (flat dose of 240mg) q2 weeks up to 3 years. Immune labs to be drawn prior to infusion on Days 1, 29 and 57.
- *Urothelial cancer patients – Nivolumab (flat dose of 240mg) q2 weeks up to 3 years or Atezolizumab (1200mg) q3 weeks up to 3 years or Pembrolizumab (flat dose of 200mg) every 3 weeks up to 3 years. Immune labs to be drawn prior to infusion on Days 1, 43 and 64.
- Radiation (10 Gy x3 fractions) will be delivered on days 1, 3 and 5.
- ‡ MRI brain for patients in the RENAL Cancer cohort only.

Table of Contents

DOCUMENT HISTORY : 6

SUMMARY OF CHANGES : AMENDMENT 1 DATED 12.15.2016 6

PROTOCOL SUMMARY 7

SCHEMA..... 9

1.0 Study Objective 13

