Eligible patients with metastatic renal cell and urothelial cancers must have at least two separate measurable sites of disease. Extent of metastatic disease is recorded by CT scanning or MRI. There are two cohorts of patients; patients with renal cell carcinoma and patients with urothelial cancers. Patients will be stratified into one of two cohorts (based on tumor type, renal cell carcinoma [cohort 1] or urothelial carcinoma [cohort 2]) and subsequently randomized to either immunotherapy without radiation (Arm A) or immunotherapy with radiation (Arm B).

In Arm A:

1. Patient with Renal Cell carcinoma will receive Nivolumab alone Days* 1, 15, 29, 43 and 57.
2. Patients with Urothelial cancer will receive either Nivolumab on Days* 1, 15, 29 43 and 57, or Atezolizumab or Pembrolizumab on Days* 1, 22, 43 and 64.

(* - infusions will have a \pm 3 days window to accommodate inevitable scheduling changes and holidays)

In Arm B:

1. Radiation is given to one lesion, 30 Gy in 3 fractions of 10 Gy each, over a one week interval (with a minimum of 36hrs between each fraction), conformally or by intensity modulated radiation treatment to maximally spare normal tissue. On the day of radiation (Day 1) immunotherapy is administered and repeated on the scheduled days. Patients will receive radiation on Day 1 and immunotherapy will be given \pm 24hr from Day 1.
2. Patient with Renal Cell carcinoma will receive Nivolumab alone Days* 1, 15, 29, 43 and 57.
3. Patients with Urothelial cancer will receive either Nivolumab alone on Days* 1, 15, 29,43 and 57 or Atezolizumab or Pembrolizumab on Days* 1, 22, 43 and 64.

(* - infusions will have a \pm 3 days window to accommodate inevitable scheduling changes and holidays)

Patients on both treatment arms will undergo re-imaging on Day 63 (\pm 7days), (Renal cell carcinoma patients should have received 5 doses; Urothelial Cancer patients should have received 3-4 doses) and every 9 weeks (\pm 7 days) for one year and every 12 weeks(\pm 7 days) thereafter.

1.10 7.0 Correlative studies

1.10.1.1 7.1 Evaluation of the cellular immune responses

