The development of immune responses to multiple tumor associated antigens has been suggested to play a crucial role in determining the therapeutic efficacy of immunotherapy.³⁶ It has been suggested that the mutational load may predict for responses to PD1/PDL1 axis blockade and may be responsible for the expression of neoepitopes necessary for the development of antitumor immunity. These immune analyses are considered exploratory and ancillary to the primary goals of the trial. The most comprehensive analysis will be based on testing the T cell and B cell response to renal cell and urothelial cancer associated tumor antigens. The advantage of this approach is the inclusion of all antigens expressed by tumors including unknown as well as cryptic epitopes.

1.10.1.2 7.2 Immune monitoring

Serial blood samples collected at baseline, and at selected time points during and post treatment will be processed to collect plasma/serum and peripheral blood mononuclear cells (PBMCs) which will be used to evaluate humoral and cellular immunity induced by PD1/PDL1 axis blockade alone vs. PD1/PDL1 axis blockade and radiotherapy.

Immune monitoring labs will be collected before each infusion on the following days.

Nivolumab patients will have immune monitoring samples on Days 1(\pm 24hrs), 29 (\pm 3days), and 57(\pm 3days)

Atezolizumab patients will have immune monitoring samples on Days 1(\pm 24hrs), 43(\pm 3days) and 64 (\pm 3days).

Pembrolizumab patients will have immune monitoring samples on Days 1 (\pm 24hrs), 43(\pm 3days) and 64 (\pm 3days).

1.10.1.3 7.3 Determine the repertoire of humoral responses induced by immunotherapy and radiation

We will use seromics technology to evaluate the repertoire of antibody responses. Seromics is an antibody profiling method utilizing protein microarrays with the capacity to detect >8000 antigens induced by a vaccine. Assays will be performed as described previously.³⁷ Plasma/serum collected at the various time points will be plated onto ProtoArrays (v4.0; Invitrogen) and incubated with fluorescent antibodies. Arrays will be scanned at 10uM resolution using microarray scanner (Axon 4200AL with GenePix Pro Software; Molecular Devices) to detect fluorescence. We will look specifically at antibodies to neoepitopes, differentiation and cancer-testis antigens, in addition to p53, survivin etc.

1.10.1.4 7.4 Determine the induction and the quality of the T cell responses in patients

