12.0 Immunological Studies

12.1 Assessment of Baseline Immune Function

Baseline cellular/humoral immune function to tumor or defined antigens will be determined for each patient from peripheral blood obtained before the administration of investigational agents (radiation and PD-1/PDL-1). For patients with accessible tumor four punch biopsies measuring approximately 4-6mm of radiated and non-radiated tumor will be obtained to prepare tumor RNA.

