15.0 Study Procedures and Observations - Nivolumab Alone and Nivolumab plus Radiation

Procedure	Screening Visit (- 28 days)	Day 1 ^h	Day 3 ^h	Day 5 ^h	Day 15 ^h	Day 29 ^h	Day 43 ^h	Day 57 ^h	Day 63 (+/-7 days)	F/UQ 9wks (±7days) for first year ^k	Follow up Q12 weeks (±7days) after 1 st year ^k years 2 and 3
Informed Consent	X										
Inclusion/Exclusion Criteria	X										
Medical History	X										
Pregnancy Test	X	X ^a				X ^a	X ^a	X ^a	X ^a		
Physical Examination Complete	X										
Physical Examination Limited		X				X	X	X	X	X	X
Vital Signs	X	X				X	X	X	X	X	X
Adverse Events Assessment	X	X				X	X	X	X	X	X
Serum Chemistry ^b	X	X				X	X	X	X	X	X
Hematology ^b	X	X				X	X	X	X	X	X
Urinalysis	X	X				X	X	X		X	X
CT (Chest, Abdomen, Pelvis) ⁱ	X								X	X ^d	Q 12 W
MRI Brain ⁱ	X										
Nivolumab infusion^j - ARM A		X			X	X	X	X			
Radiation Therapy^e - ARM B		X	X	X							
Endocrine Panels ^c	X				X	X	X	X			
Genomic Bloods/T-cell collection		X ^f				X ^f		X ^f			
Tumor biopsies	X ^g								X ^g		

a. Before each infusion.

b. SOC labs (COMP, CBC w/diff).

c. TSH, T3, T4

d. Scans day 63 ± 7.

e. Radiation is given to one, randomly selected lesion 30 Gy in 3 fractions of 10 Gy each (ARM B only)

f. to be collected PRIOR to infusion on days 1, 29 and 57.

g. Optional biopsy done at Day 63 (±7 days).

h. infusions will have a ± 3 day window.

i. prior scans will be valid until the screening period of 28 days

j. infusions will be ±24hrs from Day 1 of radiation. k. Patients will come off-study if they have disease progression. Patients will be followed for 30 days from the day they come off-study.

1.12 16.0 Study Procedures and Observations - Atezolizumab Alone and Atezolizumab plus Radiation

Procedure	Screening Visit (- 28 days)	Day 1 ^h	Day 3 ^h	Day 5 ^h	Day 22 ^h	Day 43 ^h	Day 64 ^h	Day 63 (+/-7days)	F/UQ 9wks (±7days) for first year ^k	Follow up Q12 weeks (±7days) after 1 st year ^k , years 2 and 3
Informed Consent	X									
Inclusion/Exclusion Criteria	X									
Medical History	X									
Pregnancy Test	X	X ^a			X ^a	X ^a	X ^a	X ^a		
Physical Examination Complete	X									
Physical Examination Limited		X			X	X	X	X	X	X
Vital Signs	X	X			X	X	X	X	X	X
Adverse Events Assessment	X	X			X	X	X	X	X	X
Serum Chemistry ^b	X	X			X	X	X	X	X	X
Hematology ^b	X	X			X	X	X	X	X	X
Urinalysis	X	X			X	X			X	X
CT imaging (Chest, Abdomen, Pelvis)	X							X	X ^d	Q 12 W
MRI Brain	X									
Atezolizumab/Pembrolizumab infusionⁱ - ARM A		X			X	X	X			

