Radiation Therapy^e - ARM B		X	X	X						
Endocrine Panels ^c	X				X	X				
Genomic Bloods/T-cell collection		X ^f				X ^f	X ^f			
Tumor biopsies	X ^g							X ^g		

- a. Before each infusion.
- b. SOC labs (COMP, CBC w/diff.)
- c. TSH, T3, T4
- d. Scans day 63 ± 7.
- e. Radiation is given to one, randomly selected lesion 30Gy in 3 fractions of 10 Gy each (ARM B only)
- f. to be collected PRIOR to infusion on days 1,43 and 64.
- g. Optional biopsy done at Day 63(±7 days).
- h. infusions will have a ± 3 day window.
- i. prior scans will be valid until the screening period of 28 days,
- j. infusions will be ±24hrs from Day 1 of radiation. k. Patients will come off-study if they have disease progression. Patients will be followed for 30 days from the day they come off-study.

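### The collection instructions for the Day 1 immune blood sample omit Section 12.1's pre-radiation condition, so in Arm B alone the baseline can be drawn after the first fraction

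*Combined protocol and SAP*

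**What the plan says.** **The rule.** Section 12.1 bases each patient's baseline immune function on "peripheral blood obtained before the administration of investigational agents (radiation and PD-1/PDL-1").

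**The collection instructions.** Four places tell staff when to draw, and each refers to the infusion only:
- Schema, renal cohort: "Immune labs to be drawn prior to infusion on Days 1, 29 and 57". The urothelial line has the same form with its own days.
- Section 7.2: "Immune monitoring labs will be collected before each infusion on the following days". It adds a window of ±24 hours for the Day 1 sample.
- Section 15.0, footnote f: "to be collected PRIOR to infusion on days 1, 29 and 57".
- Section 16.0, footnote f: "to be collected PRIOR to infusion on days 1,43 and 64".

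Appendix 1 lists tubes and days and says nothing about order relative to radiation.

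**Treatment timing in Arm B.** Section 6.2 states: "Patients will receive radiation on Day 1 and immunotherapy will be given" within 24 hours either side of Day 1. Footnote j in the calendars agrees: "infusions will be ±24hrs from Day 1 of radiation". The order of the two treatments within Day 1 is not given.

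**Use of the sample.** Section 7.6 defines a treatment-induced response as the difference, within a patient, between the pre-treatment value and later values. Section 29.1 compares these changes between arms with mixed models and estimating equations, and also relates T cell change to abscopal response. Specific aim 3 in Section 6.2 is the between-arm comparison of T cell induction. Section 7.1 classes all immune analyses as exploratory and ancillary.

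**The concern.** The instructions used on the day of the draw are looser than the rule they are meant to carry out, and the looseness matters in one arm only. Under footnote f, a draw just before an infusion is a valid Day 1 sample even if the patient was irradiated earlier that day or the day before. In Arm A nothing precedes the infusion, so the same instruction always gives a pre-treatment value.

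At stake is the meaning of baseline in the blood immune analyses. If some Arm B baselines already contain an early effect of radiation, that effect drops out of the measured change in Arm B and not in Arm A. Randomisation cannot balance this, because the error arises after assignment and only under one assignment. A missed pre-radiation sample cannot be taken later.

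**Working it through.** The plan gives no figure to reproduce on this point. The check sets the timing rules side by side, counts fractions, and states the form of any bias.

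**1. Can the draw follow a fraction?** Put the first fraction at hour 0.
- Infusion: from −24 to +24 hours (Section 6.2, footnote j).
- Day 1 sample: ±24 hours of Day 1 (Section 7.2) and before the infusion (footnote f).
- Second fraction: no earlier than hour 36 (Section 6.2, minimum spacing).

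| Infusion relative to fraction 1 | Fractions that can precede a draw tied to the infusion |
|---|---|
| 24 hours before | 0 |
| Same day, after the fraction | 1 |
| 24 hours after | 1, since 24 < 36 |

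Section 12.1 permits 0. One fraction is 10 of 30 Gy, or one third of the course. Footnote h, attached to the Day 1 column, says "infusions will have a ± 3 day window". A site that applied it to Day 1 could infuse at hour 72, after two fractions, whether they were given at hours 0 and 36 or on Days 1 and 3. That reading overrides the 24-hour limits, so I do not use it as the base case.

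**2. Can all the rules be met together?** Yes. A draw before both treatments satisfies Section 12.1, Section 7.2 and footnote f. The instructions therefore do not prevent a correct sample; they fail to require one.

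**3. Is there another blood baseline?** Sections 15 and 16 show the first immune draw on Day 1 and none at screening. In Appendix 1 the EDTA tubes are listed beneath a baseline heading, but the 70 mL total for the day equals 6 × 10 mL plus one serum tube (10 mL assumed). That fits a single Day 1 draw, not an earlier one. The arm-specific calendars in Section 14 are figures not available to me, so this step rests on Sections 15, 16 and Appendix 1.

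**4. Form of the bias.** Let d be the mean shift in a marker between the start of radiation and a late draw, and f the share of Arm B baselines drawn late.
- Measured change in a late-drawn patient = later value − (baseline + d) = true change − d.
- Bias in the Arm B mean change = −f × d.
- Bias in Arm A = 0, so the bias in the Arm B minus Arm A contrast is also −f × d.
- At f = 25% this is −0.25d; at f = 50% it is −0.5d; at f = 100% it is −d.

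The documents give neither f nor d. The number affected lies between 0 and 56, the planned size of Arm B. The value of d may be zero for some or all markers, and its sign decides whether Arm B change is understated or overstated.

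**5. What is not touched.** Best overall response, PFS, OS and toxicity do not use the sample. Pre-treatment biopsies sit in the screening column of both calendars, so the tissue comparisons are not exposed.

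**The case against.** The strongest reply is that the protocol already has the right rule. Section 12.1 applies to each patient and names radiation, and Section 7.6 speaks of a pre-treatment value. Footnote f is merely less specific; it does not authorise what Section 12.1 forbids. A site that irradiated first and drew blood afterwards would be in breach of the protocol. The nominal plan is same-day treatment, and the window equally allows the infusion to come first, when the problem cannot arise. The analyses are exploratory, and nothing in the documents shows that blood T and B cell responses shift within 24 hours.

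Most of this stands. A reader might infer that the plan ties the baseline to the infusion alone, or that a fully compliant site may draw it after radiation. Section 12.1 rules out both readings. A reader might also infer that all 56 Arm B baselines are compromised, or that the immune contrast is biased. The first is only a ceiling, and the second requires d to differ from zero.

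What the reply does not remove is the gap itself. All four collection instructions drop the radiation condition, and the windows printed with them fit a draw that breaks Section 12.1. A rule stated once, away from the calendar, is weak protection for a sample that cannot be repeated.

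**Conclusion.** The point holds as an inconsistency between Section 12.1 and the collection instructions, not as a design that accepts a post-radiation baseline. Staff who follow the Schema, Section 7.2 or footnote f can draw an Arm B baseline after one 10 Gy fraction; in Arm A they cannot. This could bias the exploratory comparison of change from baseline in blood immune markers by −f × d, with both terms unknown. The trial's primary and secondary results are not at risk.

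The conclusion assumes that staff work from the calendar and its footnotes, and that the Section 14 figures add no earlier immune draw. The correction is worth making because the exposure is one-sided, the sample is unrepeatable, and the change is almost free.

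**What to change.** Amend the Schema, Section 7.2, footnote f in Sections 15 and 16, and Appendix 1 to carry one condition: the Day 1 sample is drawn before both the first radiotherapy fraction and the first infusion. Replace the ±24 hours for this sample with a window that ends at the first study treatment. Leave treatment timing as it is.

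Record the time of the draw and of the first fraction. Flag any Arm B baseline drawn after a fraction, and report the blood immune change analyses with and without flagged baselines. Do not exclude them outright: only Arm B can have them, so exclusion would remove patients from one randomised arm because of an event after randomisation.

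For patients already treated, compare recorded draw times with first-fraction times before analysing change from baseline.

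The cost is wording in five places, two recorded times and one sensitivity analysis, with the same number of draws. The small downside is that the draw may move from the infusion visit to the radiotherapy visit.

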Full Title:	Phase II randomized trial of PD-1/PDL-1 axis blockade versus PD-1/PDL-1 axis blockade plus radiotherapy in metastatic genitourinary (renal/urothelial) malignancies
Short Title:	Immunotherapy Plus Radiotherapy in Genitourinary Malignancies
Clinical Phase:	Phase II
Principal Investigator:	[name], M.D. .
Sample Size:	N = 112
Accrual Ceiling:	129
Study Population:	Eligible patients have metastatic renal cell carcinoma/urothelial carcinoma with at least 2 measurable sites of disease.
Accrual Period:	We expect to accrue up to 112 patients over three years and at an accrual rate of approximately 40 patients per year.
Study Design:	Eligible patients have metastatic renal cell carcinoma/urothelial carcinoma with at least 2 measurable sites of disease. All eligible patients will be randomly assigned to immunotherapy (Nivolumab/Atezolizumab/Pembrolizumab) versus immunotherapy (Nivolumab/Atezolizumab/ Pembrolizumab) plus radiotherapy, 10 Gy x3 (conformally or by IMRT/IGRT to maximally spare normal tissue), to one of their measurable lesions. For patients assigned to the immunotherapy plus radiotherapy arm, immunotherapy treatment starts with the first radiotherapy fraction. Nivolumab will be given every 2 weeks for patients with metastatic renal cell cancer and Atezolizumab (flat dose 1200mg) or Pembrolizumab (flat dose 200mg) will be given every 3 weeks for patients with metastatic urothelial cancer. Patients will be re-imaged at 9 week (year 1) or 12 week (years 2-3) intervals and evaluated for response (defined as an objective response of measurable metastatic sites outside the radiation field). This response will be evaluated with CT scans in non-irradiated measurable metastatic sites per RECIST version 1.1. Patients will continue to receive their respective immunotherapies for up to three years or until disease progression or until a dose limiting toxicity is reached.

Study Duration: *Participants will have approximately up to 25-35/yr visits and a follow-up for up to 3 years.*

**Study Agent/
Intervention:**

Patients with metastatic renal cell carcinoma will receive Nivolumab intravenously at a flat dose of 240mg every two weeks. Infusions will be given over 60 minutes (not bolus or IV push). Patients will continue to receive infusions every two weeks for up to three years or until disease progression or until a dose limiting toxicity is reached.

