17.2 Study Drug Discontinuation

- Intercurrent illness that prevents further administration of treatment,
- Unacceptable toxicity,
- Patient decides to withdraw from the study (patients will be followed up to 30 days from the withdrawn date. If patient withdraws consent, patient will not be followed and no data will be collected), or
- General or specific changes in the patient's condition render the patient unacceptable for further treatment in the judgment of the investigator, or
- Physician's discretion, or
- Patient non-compliance

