17.3.2 Safety Assessments

All patients who receive at least one dose of Immunotherapy will be considered evaluable for safety parameters. Additionally, any occurrence of a SAE from time of consent up to and including follow-up visits will be reported. Refer to safety reporting section 6.2

Safety will be evaluated for all treated patients using the NCI CTCAE version 4.03 (<http://ctep.cancer.gov>). Safety assessments will be based on medical review of AE reports and the results of vital sign measurements, physical examinations and clinical laboratory tests.

1.12.1.1 17.4 Criteria for Evaluation

1.12.1.1.1 17.4.1 Safety Evaluation

This protocol will be monitored by the WCM Data Safety Monitoring Committee which oversees the safety of all WCM investigator initiated clinical trials. The trial will be monitored for all adverse events, laboratory abnormalities, and serious adverse events at least once every 12 months. In addition, serious adverse events are monitored for all studies on a monthly basis.

1.12.1.1.2 17.4.2 Efficacy Evaluation

For the purposes of this study, patients should be re-evaluated for response every 9 weeks, in year 1, every 12 weeks in years 2 and 3. Confirmatory scans may also be obtained 4 weeks following initial documentation of objective response or progressive disease.

Response and progression will be evaluated in this study using the international criteria proposed by the Response Evaluation Criteria in Solid Tumors (RECIST) guideline (version 1.1). Patients will be followed for scans every 9 weeks for the first year or until disease progression and every 12 weeks after the first year or until disease progression.

Measurable and non-measurable lesions:

- Measurable disease: Measurable lesions are defined as those that can be accurately measured in at least one dimension (longest diameter to be recorded) as ≥ 20 mm (≥ 2 cm) by chest x-ray or as ≥ 10 mm (≥ 1 cm) with CT scan, MRI, or calipers by clinical exam. All tumor measurements must be recorded in millimeters (or decimal fractions of centimeters).
- Malignant lymph nodes: pathologically enlarged and measurable lymph node must be ≥ 15 mm (≥ 1.5 cm) in short axis when assessed by CT scan (CT scan slice thickness recommended to be no greater than 5 mm [0.5 cm]). At baseline and in follow-up, only the short axis will be measured and followed.

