- AEs should be followed to resolution or stabilization, and reported as SAEs if they become serious. This also applies to subjects experiencing AEs that cause interruption or discontinuation of immunotherapy, or those experiencing AEs that are present at the end of their participation in the study; such subjects should receive post-treatment follow-up as appropriate.
- All SAEs must be collected which occur within 30 days of discontinuation of dosing or completion of the patient's participation in the study if the last scheduled visit occurs at a later time. In addition, the Investigator should notify WCM of any SAE that may occur after this time period which they believe to be certainly, probably, or possibly related to immunotherapy.

1.16.1.8 21.8 Pregnancy

Sexually active women of childbearing potential must use an effective method of birth control during the course of the study, in a manner such that risk of failure is minimized.

Before enrolling women of childbearing potential (WOCBP) in this clinical trial, Investigators must review the guideline about study participation for WOCBP which can be found in the GCP Manual for Investigators. The topics include the following:

- General Information
- Informed Consent Form
- Pregnancy Prevention Information Sheet
- Drug Interactions with Hormonal Contraceptives
- Contraceptives in Current Use
- Guidelines for the Follow-up of a Reported Pregnancy

Prior to study enrollment, WOCBP must be advised of the importance of avoiding pregnancy during trial participation and the potential risk factors for an unintentional pregnancy. The subject must sign an informed consent form documenting this discussion.

All WOCBP MUST have a **negative** pregnancy test within 72 hours **prior** to receiving immunotherapy. The minimum sensitivity of the pregnancy test must be 25 IU/L or equivalent units of HCG. If the pregnancy test is positive, the subject must not receive nivolumab or atezolizumab and must not be enrolled in the study.

In addition, all WOCBP should be instructed to contact the Investigator immediately if they suspect they might be pregnant (e.g., missed or late menstrual period) at any time during study participation.

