Forty patients per year will be randomized to the trial over ~ 3 years of accrual, assuming an accrual rate of approximately 20 patients per year for each cohort (see study calendar).

1.24.1.1 29.1 Statistical analysis

Both arms will run in parallel but will be analyzed separately. When the target accrual is met for a cohort, it will be closed to accrual even though other cohorts may still be accruing. Analyses will be done separately for each arm. Analyses will be similar for the two arms.

The primary objective of this study is the comparison of best overall response rates between each arm after start of treatment. Fisher's Exact test will be used to estimate 95% confidence intervals for the difference and to perform a one-sided test with an alpha level of 20%. Response rates for each arm will also be estimated at this level. With 56 patients treated under each modality, if the true responses are 20% and 40% in the immunotherapy alone and immunotherapy and radiation arms, respectively, we have a 90% probability of detecting a difference between modalities. Secondary objectives include time to disease progression and mortality. Median times for these events will be estimated with 95% confidence intervals. Graphical summaries will include Kaplan-Meier curves and log-rank tests which will be used to detect differences between treatments. Median survival and progression times will be estimated if sufficient events are observed. Cox proportional hazards regression will be used to account for baseline characteristics. Stratified exploratory analyses by type of cancer (renal cancer cell carcinoma or urothelial carcinoma) will also be performed.

Toxicities will be summarized per arm and prepared using Chi-square or Fisher's Exact tests, where appropriate.

Patient and disease characteristics will be summarized and compared at randomization between the two treatment arms using descriptive statistics and graphical displays. Although randomization will remove systematic biases we will test for differences in arms using Chi-square or Fisher's exact methods for categorical variables and t-tests or Kruskal-Wallis tests (with appropriate transformations of data if necessary for continuous variables). Differences in RECIST outcomes within each patient comparing non-irradiated and irradiated lesions will be summarized. Similar techniques will be used for exploratory analyses of the following:

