1. Distribution of changes in T cells from baseline to response evaluation.
2. Association between abscopal responses and T cell changes from baseline. Changes from baseline in immune responses will be summarized over the time course of the study and post treatment using descriptive statistics and graphical displays. The patterns of changes in immune parameters will be examined using exploratory statistical approaches to assess the relationship of changes in individual parameters to clinical outcomes. Mixed effects regression models and general estimating equations will be used to compare the patterns of change in immune response over time in the two treatment groups.

Changes from pretreatment to follow up levels of immunologic parameters and other parameters described above in irradiated tumors (and non-irradiated tumors) will be compared between the two treatment groups using descriptive statistics and graphical displays.

All patients will be followed for progression-free survival and overall survival. Kaplan-Meier curves for progression-free survival and overall survival will be provided to summarize the results.

1.24.1.2 29.2 Interim Analyses

A futility analysis will be conducted after 50% of the total 18-week RECIST responses (estimated median time to response ~14 weeks) for final analysis have occurred (i.e., N/2 of N). No accrual suspension is required to conduct the futility analysis. If at this point the relative risk of no response in the immunotherapy arm over the immunotherapy plus radiation arm is 1.0 or less, the study will be stopped for futility.

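### The calendars take patients off study at progression and follow them for 30 days only, while Section 29.1 follows everyone for overall survival; no survival contact or OS censoring rule closes the gap.

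*Combined protocol and SAP*

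**What the plan says.** - **Sections 15.0 and 16.0, footnote k** (same wording in both, attached to the follow-up columns for year 1 and for years 2 and 3): "Patients will come off-study if they have disease progression. Patients will be followed for 30 days from the day they come off-study".
- **Section 17.4.2**, on imaging: "Patients will be followed for scans every 9 weeks for the first year or until disease progression". Later scans, every 12 weeks, also run to progression.
- **Section 17.2**, for a patient who withdraws from the study: "patients will be followed up to 30 days from the withdrawn date". Patients who withdraw consent are treated separately, with no further data.
- **Section 21.7**: "All SAEs must be collected which occur within 30 days of discontinuation of dosing". Later events are reported only if judged related to immunotherapy.
- **Protocol Summary**: a secondary aim is "to estimate the median progression free survival and the median overall survival for patients treated with immunotherapy and immunotherapy plus radiotherapy". The study duration entry gives "a follow-up for up to 3 years" and mentions neither survival status nor patients who have progressed.
- **Section 29.1**: "All patients will be followed for progression-free survival and overall survival". It plans medians with 95% confidence intervals, Kaplan-Meier curves, log-rank tests and Cox models, and adds: "Median survival and progression times will be estimated if sufficient events are observed".

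**The concern.** The calendar is what a site works from. It ends a patient's time on study at progression and allows 30 more days. The analysis section assumes that the same patients are followed to death. Nothing in the readable text joins the two: no call, visit, chart check or registry check after the 30 days, and no statement of when OS is censored.

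In metastatic renal or urothelial cancer, most deaths can be expected to follow progression by more than a month. If footnote k is applied literally, those deaths fall outside the data. What remains is censored at a time fixed by progression, which is itself tied to the risk of death, so the independent-censoring assumption behind Kaplan-Meier, log-rank and Cox fails. The plan's condition for estimating medians, that enough events are seen, could also fail because of the follow-up rule and not because patients live longer.

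**Working it through.** **The plan's own figure.** The only stated design calculation concerns response: 56 per arm, 20% v 40%, one-sided alpha 0.20, power 90%. Exact enumeration of the one-sided Fisher test gives 90.2%, so it reproduces, and this point does not affect it. No OS event count, power or follow-up length is stated, so the effect on OS has to be illustrated.

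**Inputs**
- From the documents: 56 patients per arm (Section 29.0); 30 days after progression (footnote k); up to 3 years of follow-up (Protocol Summary); median OS of 25 months on nivolumab in renal cancer (Section 2.1; Table 18 in Section 3.4).
- Assumed: median PFS of 2, 4, 6 or 9 months; share q of PFS events that are deaths of 5, 10, 15 or 20%; median OS of 12 or 18 months besides 25; constant hazards. This gives 4 × 4 × 3 = 48 scenarios.

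**Model.** PFS hazard λ = ln 2 / median PFS. Death hazard before progression = qλ. Death hazard after progression = μ, chosen so that true OS equals 0.5 at the chosen median, where

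S(t) = e^(−λt) + (1−q)λ[e^(−μt) − e^(−λt)]/(λ−μ).

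Under footnote k, follow-up ends at the earlier of progression + D (D = 30/30.44 = 0.986 months) and 36 months.

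**One scenario in full** (median OS 25, median PFS 4, q = 10%)
1. λ = 0.6931/4 = 0.1733 per month; qλ = 0.0173; solving S(25) = 0.5 gives μ = 0.0314.
2. True deaths by 36 months: 1 − S(36) = 0.645, and 0.645 × 56 = 36.1.
3. Recorded deaths: before progression 0.10 × 0.998 = 0.0998; within 30 days after it 0.90 × (1 − e^(−0.0314 × 0.986)) = 0.0274. Sum 0.127, and 0.127 × 56 = 7.1. So 7.1 of 36.1 deaths are recorded (20%).
4. After the first month, the ratio of recently progressed to progression-free patients at risk is (1−q)λ[e^((λ−μ)D) − 1]/(λ−μ) = 0.165. The hazard that Kaplan-Meier sees is (0.0173 + 0.0314 × 0.165)/1.165 = 0.0193, close to the pre-progression value.
5. Kaplan-Meier OS at 24 months is about e^(−0.0193 × 24) = 0.63 (0.630 by numerical integration); the true value is S(24) = 0.516. The curve is 11 points too high.

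**All scenarios** (numerical integration)

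| Set | Deaths per 56 by 36 months | Recorded | Share recorded | Error in 24-month OS (points) |
|---|---|---|---|---|
| 41 with μ > qλ | 35.5–53.5 | 4.3–21.1 | 12%–41% | +2 to +45 |
| of these, median OS 25 (12) | 35.5–38.5 | 4.3–12.3 | 12%–34% | +2 to +32 |
| 7 with μ < qλ | 33.9–48.2 | 6.9–13.5 | 20%–36% | −26 to −6 |

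In the 41 scenarios, the Kaplan-Meier median is reached within 36 months in 27 (15 of 15 at true median 12, 8 of 14 at 18, 4 of 12 at 25), and always later than the true median.

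**Between arms.** With equal true median OS in both arms and median PFS of 4 v 6 months, the Cox hazard ratio under footnote k is 0.71–0.91 if the death share of PFS events is equal in both arms, but 0.94–1.00 if the pre-progression death hazard is equal. Full follow-up gives 1.01–1.06 and 1.01–1.04. A spurious OS difference is therefore possible, but no single size can be claimed.

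**The case against.** The strongest reply is that footnote k sits only on the two follow-up visit columns. A note placed there most naturally says when those visits stop, and 30 days matches the SAE window in Section 21.7. Section 29.1 is the passage that addresses survival follow-up, and the Protocol Summary allows up to 3 years. On that reading, the plan is under-specified and not contradictory, and the loss of deaths arises only if the footnote overrides Section 29.1. The trigger is also unclear: the off-study criteria in Section 12.3 do not list progression, and Section 20.0 keeps some patients with tumour increase before week 12 on treatment and imaging. The schema and the Section 14.0 graphics are not shown and could hold a survival row.

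The benign reading may well be what was intended. But the footnote says that patients leave the study, not that visits end, and neither it nor Section 17.2 limits the 30 days to safety. Even on the benign reading, the plan does not say how survival status is obtained after progression or where OS is censored. A survival row in a missing graphic would still conflict with the footnote. Sections 12.3 and 20.0 are further passages to reconcile with footnote k; they do not resolve it.

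The objection on numbers stands in part. PFS, death share and hazard shape are assumptions, and the upward bias in the 41 scenarios follows from the condition that selects them. Over all 16 scenarios at median OS 25, the error runs from −26 to +32 points. The direction is therefore conditional; the loss of most deaths is not, since it appears in all 48.

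**Conclusion.** The concern holds: this should be fixed, but it does not threaten the primary comparison. The conflict between footnote k and Section 29.1 is plain from the text, and the readable text has neither a survival contact after progression nor an OS censoring rule. If the calendar is followed literally, only 12% to 41% of the deaths within 36 months are recorded across all 48 assumed scenarios. Kaplan-Meier OS is too high where the death hazard rises after progression, which is the expected case, and too low where it does not. These sizes rest on constant hazards and on assumed PFS, death shares and, apart from 25 months, median OS. OS is a secondary endpoint with no event target, and the response endpoint and its power are untouched.

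**What to change.** 1. In footnote k of Sections 15.0 and 16.0, state that progression ends the scheduled study visits only. State there and in Section 17.2 what the 30 days are for (for example, the safety window).
2. Add to Section 29.1: vital status and date of death are collected by chart review or phone, for example every 12 weeks, up to the planned 3 years, for every randomised patient who has not withdrawn consent; OS is censored at the date last known alive.
3. In the same amendment, reconcile footnote k with Sections 12.3 and 20.0 on when progression takes a patient off study.

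The cost is amendment wording and a little coordinator time: at most 156/12 = 13 checks per patient, fewer in practice because they start after progression and stop at death. No visits, scans or procedures are added. The consent form must allow the contact; its pages were not in the text reviewed. The 12-week interval is a suggestion; the essential parts are a defined contact and a censoring rule.
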